Study objectives	
Primary Objective
 
Absolute pain score 24h after surgery, assessed by 100mm visual analogue score (VAS).
 
Secondary Objectives
 
Minimal Clinically Important Difference [MCID] in visual analogue score; VAS adjusted for pain severity; postoperative morbidity; opioid use; heart rate variability [explanatory variable].

Study design	Phase II, single-centre, two-arm, parallel group randomised controlled trial
Setting	Surgical services of hospitals undertaking major trauma orthopaedic surgery.
Participants	
Inclusion criteria
 
 • Scheduled to undergo major elective or urgent (not requiring intervention in <24h) noncardiac (orthopaedic) surgery under general and/or spinal anaesthesia, expected to take >120 minutes from the induction of anaesthesia. • American society of Anaesthesiologists (ASA) grade I–III. • Aged 18 years and over. 
Exclusion criteria
 
 • Requiring invasive mechanical ventilation and/or new renal replacement therapy during hospitalization. • Cardiac arrhythmia requiring therapy prior to/during hospitalization. • Dementia. • Cancer requiring active/ongoing therapy. • Postural orthostatic tachycardia syndrome. • Lower limb neuromuscular disorders. • Auricular dermatitis. • Day-case surgery, not requiring overnight hospital admission.
Interventions	
Sham Group: Patients randomised to receive sham treatment will receive no current via the bilateral auricular leads for 50 minutes.
 
Stimulation Group: Patients randomised to receive stimulation will receive a sub-threshold current via the bilateral auricular leads for 50 minutes.

Primary outcome measure	The primary outcome is absolute pain score 24h after surgery, assessed using the 100mm visual analogue score.

Outcome measures

Primary outcome measure

The primary outcome will be the absolute VAS pain score 24h after surgery.

Secondary outcome measures

Minimally Clinical Important Difference: The proportion of participants who achieve a minimally clinical relevant reduction >10mm using the 100 mm pain Visual Analogue Score will be compared before and after the period of stimulation in each group, before and after surgery.[1]

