VAS stratified by pain intensity: Absolute changes in pain score before and after sham/stimulation will be compared before and after the period of stimulation in each group before and after surgery, stratifying for mild, moderate, and severe pain intensity before the intervention. A pain VAS score of 30, 70, and 100 indicates the upper boundaries of mild, moderate, and severe pain intensity.[1]

Postoperative morbidity: Defined by the Post Operative Morbidity Survey (POMS) before (preoperative) and after (postoperative days 3 and 7) surgery. The POMS is an 18-item survey which examines nine domains (pulmonary, infection, renal, gastrointestinal, cardiovascular, neurological, haematological, wound, pain) of postoperative morbidity.[2] The POMS is a reliable and valid measure of short-term postoperative morbidity following major surgery.²⁰ The hospital electronic patient management system will be used to prospectively record POMS on postoperative days 0 (preoperative), 3 and 7. Clavien-Dindo grades for complications during hospital stay will also be reported.

Opiate use: Opiate consumption [expressed as morphine equivalents] before and for three days after surgery.

Explanatory measures

Autonomic function, as assessed by time and frequency domain measures of heart rate variability 10 minutes before and 10 minutes after each stimulation session, before and after surgery.[3]

Sample size and randomisation

Sample size calculation

Consensus perioperative guidelines recommend that the Visual Analogue Score should be used to assess pain intensity.[4] 72 patients are required to have a 90% chance of detecting, significant at the 1% level, a decrease in mean VAS (the primary outcome measure) from 34mm in the control group to 23mm in the experimental group after surgery (standard deviation of outcome 12mm). Allowing for 10% dropout per group, a final sample size of 86 participants is required, analysed by intention to treat.

Randomisation procedure

Randomisation will occur after the participant has provided informed consent before the surgical procedure is due to start. Participants are randomly assigned (1:1) by block randomisation to receive stimulation or sham stimulation to ensure a balance in sample size across groups over time (Power

Analysis & Sample Size (PASS) 2021, Utah, USA). Investigators will log on to a secure web-based randomisation file to obtain a unique patient identification number and allocation to a treatment group.

Analysis methods

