General analysis principles

Analyses will follow the intention-to-treat principle: all randomised patients with a recorded outcome will be included in the analysis and analysed according to the treatment to which they were randomised [5, 6]. Patients will be included in the analysis, regardless of whether the treatment they received was compliant with the protocol. Definitions of what constitutes a recorded outcome for each outcome can be found in Appendix 1. Patients with missing outcome data will be excluded from the analysis. Missing data for baseline covariates to be included in the analysis model will be accounted for using mean imputation for continuous variables and the missing indicator approach will be used for missing data for categorical variables [7, 8].

For the analysis of the primary outcome, each secondary outcome, and all process measures, we will present the following information:

The number of patients included in each analysis, by treatment group

A summary statistic of the outcome (e.g. mean (SD), number (%)), by treatment group

The estimated treatment effect

A 95% confidence interval for the estimated treatment effect

A two-sided p-value

For all analyses, a significance level of 5% will be used.

Representativeness of patients

A log of eligible patients not recruited to the trial will be kept. Reasons for non-participation will be categorised and summarised. Participation in the trial, treatment allocation and completeness of follow-up will be illustrated by a CONSORT flow diagram [9].

Baseline characteristics

Baseline characteristics will be summarised for each treatment group by the mean and standard deviation or median and interquartile range for continuous variables, and the number and percent for categorical variables. The following baseline characteristics will be summarised by treatment group:

- Demographic: age (years), gender (male/female)
- Co-morbid disease: Hypertension; Ischaemic heart disease; Cardiac failure; Cardiac valvular disease
- Stroke/TIA; Peripheral vascular disease; Diabetes mellitus, type I; Diabetes mellitus, type II ; COPD; Asthma
Smoker; Interstitial or other respiratory disease; Liver cirrhosis; GI pathology-other; Osteoarthritis;
Rheumatoid arthritis; Inflammatory disease; Active cancer; Previous cancer
- ASA grade

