- Medications: Statin; Anticoagulant; Antiplatelet; Beta-blocker; Calcium channel antagonist; Heart rate limiting calcium channel antagonist; Doxazosin; Diuretic; Nitrate; Angiotensin converting enzyme inhibitors; Angiotensin II Receptor Blockers; Other hypertensives; Other heart failure Rx; Digoxin/anti-arrhythmic; Other Rx Asthma Rx; Opioids-oral; Opioids- parental; NSAIDs; Paracetamol' Steroids; Metformin; Insulin; Any other diabetic medication
- Pre-operative blood test results (within 1 week before surgery or most recent): Haemoglobin; Serum Albumin; Creatinine; white cell count; Neutrophil count; Lymphocyte count; CRP
- Anxiety: GAD-7 and Amsterdam preoperative anxiety score.

Analysis software

All analyses will be conducted in NCSS 2021 (NCSS 2021 Statistical Software (2021). NCSS, LLC. Kaysville, Utah, USA, ncss.com/software/ncss).

Analysis of primary outcome

Primary analysis

Difference in absolute pain score 24h after surgery, assessed by 100mm visual analogue score (VAS), under the ITT principle [10]. Repeat-measures ANOVA will be used to compare VAS before versus after stimulation/sham, with post hoc Tukey-Kramer testing.

Analysis of secondary outcomes

Minimally clinical relevant reduction before and 24h after surgery: The proportion of participants who achieve a minimally clinical relevant reduction >10mm using the 100 mm pain Visual Analogue Score will be compared before and after the period of stimulation in each group, before and after surgery.[1] Paired t-test will compare between sham and stimulation groups.

VAS stratified by pain intensity: Absolute changes in pain score before and after sham/stimulation will be compared before and after the period of stimulation in each group before and after surgery, stratifying for mild, moderate, and severe pain intensity before the intervention. Repeat-measures ANOVA will be used to compare VAS before versus after stimulation/sham, with post hoc Tukey-Kramer testing.

Postoperative morbidity: Absence of POMS will be compared between groups serially [time to become free of morbidity after surgery]. Individual POMS will be reported in a separate table but not tested formally.

Opiate use: Opiate consumption [expressed as morphine equivalents] will be presented before and for three days after surgery, between stimulation/sham, but not tested formally.

Explanatory measures

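### The primary analysis is a before-versus-after ANOVA that designates no between-arm contrast of 24h VAS, although that contrast is the stated outcome and the basis of the sample size

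*SAP*

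**What the plan says.** The trial is described as a "Phase II, single-centre, two-arm, parallel group randomised controlled trial". Under Primary outcome measure: "The primary outcome will be the absolute VAS pain score 24h after surgery". Appendix 1 adds only the 0 to 100 mm scale.

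The Sample size calculation rests on "a decrease in mean VAS (the primary outcome measure) from 34mm in the control group to 23mm in the experimental group after surgery", with an outcome SD of 12 mm, 90% power and a 1% level, giving 72 patients.

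General analysis principles promises a treatment effect, a 95% confidence interval and a two-sided p-value at a 5% level. Table 4 has matching columns for the 24h VAS row. The same section gives rules for "Missing data for baseline covariates to be included in the analysis model", but no analysis in the SAP names a covariate.

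Primary analysis opens by naming the difference in 24h VAS under intention to treat. Its only statement of method is: "Repeat-measures ANOVA will be used to compare VAS before versus after stimulation/sham, with post hoc Tukey-Kramer testing". The same sentence is used for the secondary analysis of changes stratified by pain intensity. The heart rate variability analysis, in contrast, writes out its factors, including group.

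**The concern.** The outcome and the sample size concern one comparison between randomised arms at one time. The method sentence names a comparison between two times. Pain can change across a 50-minute session for reasons that sham patients share, so a before-after change does not show an effect of stimulation.

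If the ANOVA is meant to include group, it yields a group effect, a time effect, an interaction and a set of Tukey-Kramer pairs. The SAP does not say which of these fills the treatment-effect column of Table 4. A before/after layout also implies two readings around the postoperative session, and the SAP does not say which of them is the 24h VAS. Both choices could then be made after the data are seen.

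**Working it through.** **Inputs.** From the Sample size calculation: difference 34 − 23 = 11 mm, SD 12 mm, 72 evaluable patients, hence 36 per arm at 1:1. From General analysis principles: two-sided 5%. Assumed, because the SAP gives no figure: within-patient correlation ρ of 0.3, 0.5 or 0.7, and 4 or 8 cells in the ANOVA.

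**1. Reproduce the plan's figure.** For two independent means at two-sided 1% and 90% power, n per arm = 2(2.576 + 1.282)² × 12² / 11² = 35.4, rounded up to 36, or 72 in total. One-sided 1% would give 62 and two-sided 5% would give 52. The trial was therefore sized on the between-arm difference, using the SD of the outcome and not of a change.

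**2. The direct 24h contrast.** Standard error = 12 × √(2/36) = 2.828; noncentrality = 11 / 2.828 = 3.889. With the noncentral t on 70 degrees of freedom, power is 97.0% at 5% and 88.9% at 1%.

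**3. The literal reading: a time effect only.** Suppose both arms fall from 34 to 23 mm with no difference between them. The standard error of the mean change is 12 × √(2(1 − ρ)/72) = 1.414 at ρ = 0.5, and 11 / 1.414 = 7.8. In 20,000 simulated trials at each ρ, the before-after test was significant in about 100%, and the between-arm test at the final reading in about 5%. Now suppose the arms differ by 11 mm at both readings with no change over time. The before-after test rejects in about 5%, the between-arm test in about 97%. The two tests answer different questions.

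**4. Group factor inferred.** Take the arms as equal at the first reading and 11 mm apart at the second. Power at two-sided 5%:

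| Candidate for primary result | Effect and SD | ρ = 0.3 | ρ = 0.5 | ρ = 0.7 |
|---|---|---|---|---|
| Group-by-time (difference in change) | 11 mm; 12√(2(1 − ρ)) | 90.0% | 97.0% | 99.9% |
| Group main effect (mean of both readings) | 5.5 mm; 12√((1 + ρ)/2) | 66% | 60% | 55% |
| ANCOVA on the first reading | 11 mm; 12√(1 − ρ²) | 98.0% | 99.3% | above 99.9% |

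The main effect loses power because averaging in the first reading halves the difference: 11 / 2 = 5.5 mm.

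**5. The 24h pair under Tukey-Kramer.** The critical t is the studentized range quantile divided by √2, on 70 degrees of freedom.
- 4 cells (6 pairs): critical t 2.63, per-pair level about 0.0104, power 89.2%.
- 8 cells (28 pairs): critical t 3.12, power 77.3%. With 210 degrees of freedom the critical t is 3.06 and power about 79%.

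**The case against.** The SAP does state what it wants to estimate: the opening of Primary analysis, Appendix 1 and Table 4 all name the 24h VAS. A group factor is probably intended, since the sentence mentions both treatments, Tukey-Kramer has nothing to adjust with only two levels, and the heart rate variability model includes group. With group in the model, the 24h contrast can be extracted. This stands, and it limits the point: the fault is an undesignated contrast, not an estimate that cannot be had. It does not remove the point, because the group factor has to be inferred and the primary term or pair is still not named.

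Three stronger inferences are not supported:

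- *That Tukey-Kramer necessarily costs power against the design.* With 4 cells the per-pair level of 0.0104 is practically the 1% sizing level, and 89.2% compares with 88.9% for a plain t-test at 1%. Only the 8-cell layout loses power, and the SAP does not state the number of cells.
- *That patients who stop therapy drop out of the analysis.* Nothing says that they lack a later VAS. The SAP includes patients regardless of compliance if the outcome is recorded, and plans a sensitivity analysis when more than 5% of primary data are missing.
- *That the planned test often shows a change in one arm only when there is no treatment effect.* A rate of 41 to 50% can be obtained, but for separate unadjusted paired tests within each arm, with a common fall of 3 to 4 mm and correlations of 0.5 to 0.7. The SAP does not specify those tests.

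It is also fair that ANCOVA is not the only valid repair. Designating the 24h arm contrast, or a two-sample t-test, would also remove the ambiguity.

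**Conclusion.** The point holds. Followed literally, the primary method tests a within-patient change that is not a treatment effect. Read generously, it leaves the primary result and the primary reading undefined. At the planning values the candidate tests range from about 55% power (group main effect, ρ = 0.7) to 99.9% (group-by-time, ρ = 0.7), with the direct contrast at 97%. The spread depends on the assumed correlations, the assumed cell layouts and equal arms at the first reading. The mismatch between the stated outcome and the stated method depends on none of these.

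A reader might infer that the trial is underpowered or cannot yield its primary estimate. The document does not support that: 72 evaluable patients are enough for the direct contrast, and the SAP states the intended difference. This should be settled before unblinding, because it determines what the trial reports as its main result.

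**What to change.** Replace the method sentence under Primary analysis with wording such as:

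> Linear regression (ANCOVA) of VAS 24h after surgery on randomised arm, adjusted for VAS before the first preoperative session. The arm coefficient, with its 95% confidence interval and two-sided p-value, is the primary result.

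In addition:
- State in Appendix 1, before unblinding, which single reading is the 24h VAS. The reading after the postoperative session is one option, since both sessions can affect it.
- Handle a missing baseline VAS by the mean imputation already planned. This also gives the covariate rule a model to apply to.
- Keep the repeated-measures ANOVA with Tukey-Kramer as a supportive analysis, with its factors written out as they are for heart rate variability.

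Power at 5% is then about 98 to 99.9% for baseline correlations of 0.3 to 0.7, so the sample size need not change. The cost is SAP wording only: the before-session VAS is already part of the planned before/after comparisons, and regression is a standard analysis that needs no new software.

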Appendix 1: Derived outcomes and variables

Variables

Primary outcome

VAS 24h after surgery: Expressed as 0-100mm.

Secondary outcomes

Minimally Clinical Important Difference: Expressed as 0-100mm.

[figure not shown]
VAS stratified by pain intensity: Expressed as 0-100mm.

Postoperative morbidity: 18-item survey reporting nine domains (pulmonary, infection, renal, gastrointestinal, cardiovascular, neurological, haematological, wound, pain) of postoperative morbidity.[2]

Opiate use: Opiate consumption – morphine equivalents [mean SD]

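### Preoperative MCID responder outcome: patients with a pre-session VAS of 10 mm or less can only be failures, so a comparison restricted to those able to respond should be pre-specified beside the all-randomised one (minor)

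*SAP*

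**What the plan says.** Under Analysis of secondary outcomes, the SAP states: "The proportion of participants who achieve a minimally clinical relevant reduction >10mm using the 100 mm pain Visual Analogue Score will be compared", and continues: "before and after the period of stimulation in each group, before and after surgery.[1] Paired t-test will compare between sham and stimulation groups". The rule therefore applies once to the preoperative session and once to the postoperative session.

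The analysis set comes from General analysis principles: "all randomised patients with a recorded outcome will be included in the analysis and analysed according to the treatment to which they were randomised". No outcome is exempted and no minimum baseline pain is set.

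The inclusion criteria admit patients "Scheduled to undergo major elective or urgent (not requiring intervention in <24h) noncardiac (orthopaedic) surgery under general and/or spinal anaesthesia", with further conditions on duration, ASA grade and age. None of the listed criteria asks for a minimum VAS or for pain at entry.

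Appendix 1, to which the SAP refers for outcome definitions, says of this outcome only: "Minimally Clinical Important Difference: Expressed as 0-100mm". A figure that follows this line is not shown in the text available.

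The pain-intensity strata belong to a different secondary outcome, absolute change in VAS: "A pain VAS score of 30, 70, and 100 indicates the upper boundaries of mild, moderate, and severe pain intensity.[1". The mild stratum has no lower limit, so 0-10 mm is pooled with 11-30 mm.

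**The concern.** On a scale that stops at zero, a fall of more than 10 mm is impossible from 10 mm or below. At the preoperative session the rule treats these four patients as follows:

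- 40 to 25 mm: responder.
- 8 to 0 mm, complete relief: failure.
- 0 to 0 mm, nothing to relieve: failure.
- 8 to 60 mm, worse: failure.

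The reported proportion therefore mixes two things: whether the session reduced pain, and how many enrolled patients had enough pain for a reduction to be counted. Patients who could not respond add to the denominator in both arms but carry no information about response.

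At stake are the size of the absolute responder difference and some power for this outcome. The SAP's exploratory analysis, which relates autonomic parameters to achieving MCID irrespective of allocation, uses the same classification. That analysis is not protected by randomisation. If pain before the session is itself related to heart rate variability, counting painless patients as treatment failures could produce or hide an association that has nothing to do with response.

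**Working it through.** **The plan's own figure.** The SAP gives no responder rate and no sample size for MCID. Its only VAS distribution is in the sample size section: postoperative control mean 34 mm, experimental mean 23 mm, SD 12 mm, with "72 patients are required to have a 90% chance of detecting, significant at the 1% level". That calculation reproduces: n per arm = 2 × (12/11)² × (2.576 + 1.282)² = 35.4, rounded up to 36, so 72 in total (two-sided 1%).

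**Step 1, the floor.** With pre-session VAS b, the largest possible fall is b. If b ≤ 10, the fall is at most 10, which is never greater than 10. Such a patient is a failure with certainty.

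**Step 2, dilution.** Let f be the share at 10 mm or less, equal in both arms, and let p1 and p0 be the responder rates among patients able to respond.

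- Observed rates: (1 − f)p1 and (1 − f)p0.
- Observed difference: (1 − f)(p1 − p0).
- Observed risk ratio: p1/p0, unchanged.
- If p1 = p0, the observed rates are equal, so the test keeps its validity under the null.

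**Step 3, what is known about f.** There is no preoperative VAS in the SAP. If the postoperative control planning values are borrowed and normality assumed, f = Φ((10 − 34)/12) = Φ(−2) = 2.3%. This is a reference point only. Before surgery f could be lower or higher: the setting is major trauma orthopaedic surgery, but elective patients are also eligible.

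**Step 4, size over a range.** Assumptions: p1 = 60%, p0 = 25%, 86/2 = 43 per arm, and a two-sided 5% pooled z-test with power by exact binomial enumeration. Restricted n per arm is 43(1 − f), rounded. With f = 0, power is 92.4%.

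| f | Observed rates | Difference (points) | Power, all patients (43 per arm) | Power, VAS >10 mm only (n per arm) | Cost of the all-patients denominator |
|---|---|---|---|---|---|
| 2.3% | 58.6% vs 24.4% | 34.2 | 91.5% | 92.7% (42) | about 1 point |
| 10% | 54% vs 22.5% | 31.5 | 87.7% | 89.7% (39) | about 2 points |
| 25% | 45% vs 18.75% | 26.25 | 76.4% | 84.2% (32) | about 8 points |
| 50% | 30% vs 12.5% | 17.5 | 52.9% | 66.2% (22) | about 13 points |

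The restricted power at f = 2.3% lies slightly above the f = 0 value only because an exact binomial test is discrete.

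**Step 5, separating the two causes.** The fall from 92.4% has two parts: fewer patients with pain to reduce, which no denominator can repair, and the denominator itself.

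| f | Total fall | Fewer patients in pain | Denominator |
|---|---|---|---|
| 10% | 92.4 − 87.7 = 4.7 | 92.4 − 89.7 = 2.7 | 2.0 |
| 25% | 92.4 − 76.4 = 16.0 | 92.4 − 84.2 = 8.2 | 7.8 |
| 50% | 92.4 − 52.9 = 39.5 | 92.4 − 66.2 = 26.2 | 13.3 |

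Only the last column is attributable to the rule.

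**Step 6, other assumed values.** With 36 per arm (the evaluable number before the dropout allowance), 50% vs 20% among patients able to respond and a two-sided 5% test, power for all patients against restricted is 70% vs 73% at f = 10%, 55% vs 61% at f = 30%, and 39% vs 47% at f = 50%. The pattern is the same.

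**The case against.** The strongest reply is that the all-randomised proportion is a legitimate estimand. It answers what share of enrolled patients gain a worthwhile fall, and it follows the SAP's intention-to-treat principle. This stands, and it is why that proportion should continue to be reported. It does not answer whether the session works in patients who have pain, and the SAP gives the reader no means of telling the two questions apart.

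The size rests on assumptions. This also stands: under the only VAS distribution in the SAP, f is about 2% and the gain is negligible. A reader might infer from the elective eligibility that many patients will be painless before surgery. The document gives no figure for that, and its setting points to trauma patients, who may have considerable pain.

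A reader might infer that the between-arm comparison is biased. Steps 1 and 2 do not support that. A chance imbalance in painless patients is ordinary baseline imbalance, which the p-value already allows for.

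The stratified absolute-change outcome would register a fall from 8 to 0 mm as benefit. That is partial cover only: it is a different outcome, and its mild stratum does not isolate 0-10 mm.

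Treating 8 to 0 and 8 to 60 alike is partly a property of any dichotomised outcome. Restriction does not remove it above 10 mm, where 15 to 6 and 15 to 60 are both failures.

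Finally, the power figures use a pooled z-test and all 86 patients, whereas the SAP names a paired t-test and allows for dropout. They show the cost of the denominator and are not the power of the analysis as written.

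**Conclusion.** The point holds as a cheap, minor improvement. That a patient at 10 mm or less before the preoperative session must be a failure is certain from the wording, and nothing in the visible text of Appendix 1 separates these patients; the figure not shown there could not be checked. The absolute difference shrinks by (1 − f). The avoidable power cost is about 1 to 13 points for f between about 2% and 50%, given the assumed 60% vs 25%, 43 per arm and a pooled z-test. The true f before surgery cannot be derived from the SAP.

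Two stronger readings are not supported. First, the whole fall in power should not be charged to the rule: in each case in Step 5 more than half of it comes from having fewer patients with pain. Second, the point does not reach the primary outcome or the sample size, which are postoperative. It affects one session of one secondary outcome and the preoperative part of the exploratory MCID analysis. In the exploratory analysis the misclassification matters somewhat more, because randomisation does not protect it.

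**What to change.** For the preoperative session, pre-specify in Analysis of secondary outcomes and in Appendix 1:

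1. an MCID comparison among randomised patients with pre-session VAS above 10 mm, analysed in the arm to which they were randomised;
2. the all-randomised proportion reported alongside it;
3. the number of patients at 10 mm or less, by arm.

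Use the same restriction for preoperative data in the exploratory analysis of autonomic parameters against MCID.

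The restriction uses a value taken before any stimulation, so it preserves the randomised comparison. Do not restrict the randomised comparison at the postoperative session: the VAS before that session is measured after randomisation and may already have been affected by the first session, so selecting on it could make the arms non-comparable.

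The cost is a few lines of SAP text and an added row or column in dummy Table 4, with no new data. The downside is a smaller analysed number for the restricted comparison and a second reported estimate for one secondary outcome. The denominators should be fixed before unblinding, since a choice made after seeing the data would be open to challenge.

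### The preoperative MCID responder comparison leaves out the pre-session VAS, a pre-treatment covariate already collected; the cost is some precision in a secondary outcome, not bias

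*SAP*

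**What the plan says.** Under Analysis of secondary outcomes, the SAP defines a responder by a VAS fall across a session and takes "The proportion of participants who achieve a minimally clinical relevant reduction >10mm" at the session before surgery and again at the session after it. The only method named for the arm comparison is "Paired t-test will compare between sham and stimulation groups". No covariate is given.

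General analysis principles sets imputation rules that open with "Missing data for baseline covariates to be included in the analysis model", but no analysis in the SAP says which covariates those are.

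Starting pain is used in one place only. The next secondary outcome, absolute VAS change, is analysed by "stratifying for mild, moderate, and severe pain intensity before the intervention". That does not extend to the responder proportion.

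Under Randomisation procedure, "Participants are randomly assigned (1:1) by block randomisation"; no stratification by pain is stated.

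**The concern.** A responder is defined by a fall from the pre-session VAS, so that score is part of the outcome's own definition. A patient who starts at or below 10 mm cannot fall by more than 10 mm. If there is regression to the mean, patients who start high are also more likely to fall by that much than patients who start low, whatever their arm.

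At the preoperative session the score is measured before any stimulation, which makes it a legitimate covariate, and every patient with a responder status must have it. Leaving it out means that a chance difference in starting pain between arms passes into the responder gap, and that explainable variation stays in the standard error. In a trial with 72 evaluable patients a responder gap is imprecise to begin with.

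The point survives correction of the paired t-test. A chi-squared test or a raw risk difference would still ignore starting pain.

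**Working it through.** **The plan's own figure.** The SAP states no sample size, responder rate or variance for the responder comparison. Its calculation for the primary outcome does reproduce. It says "72 patients are required to have a 90% chance of detecting, significant at the 1% level", for a change "from 34mm in the control group to 23mm in the experimental group after surgery" with "standard deviation of outcome 12mm". Two-sided at 1%:

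n per arm = 2 × (12/11)² × (2.576 + 1.282)² = 35.4, rounded up to 36, or 72 in total.

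These are postoperative planning values. Using 34 mm and 12 mm for the preoperative session is an assumption.

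**Assumed inputs (none is in the SAP for this session).**
- Pre-session VAS: mean 34, SD 12; alternatively mean 30, SD 20.
- Pre/post correlation r: 0.5, 0.7, 0.9.
- Mean fall without active treatment 4 mm; stimulation effect 6 mm.
- 38 patients per arm (43 randomised per arm × 0.9 = 38.7).
- Regression-to-the-mean model, scores bounded at 0 and 100: post = mean − 4 − effect + r × (pre − mean) + SD × √(1 − r²) × e, with e standard normal.

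**Step 1: does starting VAS predict response?** At mean 34, SD 12, with no active treatment and r of 0.5-0.7, the responder probability is 8-9% for starters at 10-20 mm and 37-47% for starters at 40-50 mm. The floor contributes little: P(VAS ≤ 10) = Φ((10 − 34)/12) = Φ(−2), about 2%. With a preoperative mean of 23 it would be Φ(−1.08), about 14%.

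**Step 2: what does a chance imbalance do?** The SD of the difference in mean starting VAS between arms is 12 × √(2/38) = 2.75 mm.

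| Higher start in one arm | Responder rate, r = 0.5 | Responder rate, r = 0.7 |
|---|---|---|
| 0 mm | 30.8% | 25.8% |
| 2.75 mm (1 SD) | 34.9% (+4.1 points) | 28.8% (+3.0) |
| 5 mm (5/2.75 = 1.8 SD) | 38.5% (+7.7) | 31.4% (+5.6) |

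Over a wider grid (mean 15-45, SD 12-25, r 0.5-0.9, 36 per arm), an imbalance of one standard error moves the gap by about 1-7 points, mostly 3-5. The gap's own standard error is about 9-11 points.

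**Step 3: what does adjustment gain?** Reduction in the variance of the risk difference, from simulated trials with linear adjustment for pre-session VAS. The average risk difference did not change. Repeat runs differ by a point or two.

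| Setting | r = 0.5 to 0.7 | r = 0.9 |
|---|---|---|
| Mean 34, SD 12 | 8-14% | within 2-8% |
| Mean 30, SD 20 | 14-21% | within 2-8% |
| Fall unrelated to starting VAS | about 0-3%; a loss of 1-2% at mean 34, SD 12 | the same |

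A variance cut of 8-21% multiplies the standard error by √0.92 = 0.96 to √0.79 = 0.89. Put another way, 72 patients would give the precision of 72/0.92 = 78 to 72/0.79 = 91.

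**Cross-check.** The variance ratio should be near 1 − R², where R² is from the within-arm regression of responder status on pre-session VAS. A separate large simulation at mean 34, SD 12, with an 11 mm effect, gives R² of 15%, 9% and 4% at r = 0.5, 0.7 and 0.9, in line with the first row. Across all the models tried, including proportional and purely additive effects, R² ran from about 0 to 42%.

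**The case against.** The strongest reply is that nothing here is wrong. Allocation is randomised, so an unadjusted difference in proportions is unbiased, and a valid confidence interval already allows for chance imbalance. This stands. A reader might infer that the responder result is biased towards the arm that starts with more pain. The SAP does not support that: such an imbalance is ordinary sampling error, and a one-SE imbalance is well within the gap's own standard error.

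A reader might also infer that starting pain largely settles who responds, or that a fixed share of the variance, such as 10-20%, is being left on the table. Neither follows. Where the covariate explains 10-20%, 80-90% is unrelated to it. The SAP gives none of the quantities that would fix the share. The two readings bracket a 50-minute session, so their correlation could well exceed 0.7, where the gain is small. If the fall does not depend on starting VAS, only patients near the floor are affected.

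Three further replies are fair. The MCID proportion is one of several secondary outcomes. The SAP does examine dependence on starting pain, through the stratified VAS-change analysis. And the paired t-test across independent arms is the larger fault in the same paragraph.

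None of this supplies a reason to leave the covariate out. The stratified analysis concerns a different outcome, and the test has to be rewritten in any case.

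**Conclusion.** The point holds as an optional gain in efficiency. The preoperative responder comparison omits a covariate that is already collected, precedes treatment and is likely to be prognostic. The expected gain is a cut of roughly 8-21% in the variance of the risk difference if the preoperative mean is 30-34 mm, the SD 12-20 mm, the correlation 0.5-0.7 and scores regress to the mean. It is about 2-8% at correlation 0.9 and about zero if the fall is unrelated to starting VAS. All of these inputs are assumptions.

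A reader might extend the same gain to the session 24h after surgery. Nothing has been quantified for that session, and the VAS taken just before it follows the first treatment, so the argument does not carry over.

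There is a secondary benefit. The SAP refers to covariates without naming any, so naming this one in advance removes a later choice between adjusted and unadjusted results.

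**What to change.** When the paired t-test is replaced by a method for independent proportions, add that the arm difference at the preoperative session will be estimated by logistic regression on arm and pre-session VAS (continuous), reported as a standardised risk difference with 95% CI, with the raw proportions beside it.

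If the 24h responder comparison is also adjusted, use the VAS taken before the first session. Do not use the 24h pre-session VAS, which may already carry a treatment effect.

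The cost is a sentence or two of SAP text and no new data. The downside is small: a model-based estimate takes the place of a simple difference in proportions, and the gain may prove negligible.
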